 - This can be collected anytime during the screening period or on the day of the screening colonoscopy, prior to blinded FMT treatment, but if the subject is randomized to receive psyllium fiber, then this should be collected before day -3 when they begin the fiber supplementation.

*: These standard of care laboratory tests must be done during the screening period. However, if the subject consents on page 5 of the informed consent form then recent laboratory results may instead be used if the subject had them conducted as standard of care within 2 weeks of signing consent.

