6.1.2.1 Screening Colonoscopy (Baseline, Week 0 Day 0)

- Urine pregnancy test as standard of care
- Standard of Care Colonoscopy for diagnostic purposes
 1. Mucosal biopsies taken for diagnostic and research purposes
- FMT delivery by colonoscopy for research purposes

1. If active disease, study physician will blindly administer placebo or investigational FMP250
- Stool and blood samples taken for research purposes, if not previously collected during screening period (days -28 to -3).

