7.8 Dosing and Administration

7.8.1 FMP250

Prior to colonoscopy subjects will be asked to undergo bowel prep and to fast the night before the procedure. Additionally, subjects will be provided anti-diarrheal agent(s) 1-2 hours prior to the procedure to aid with retention of the fecal transfer, which ideally would be for up to four hours.

The study intervention will only be infused through the working channel of the instrument during colonoscopy at the day 0 screening visit if the clinician confirms the subject meets the endoscopy dependent inclusion criteria. A 250cc dosage of the investigational or placebo FMP250 will be delivered in aliquots of 60cc but we also recognize that some fecal material may be lost during the transfer. During the week 8 flexible sigmoidoscopy, subjects that were randomized into the placebo group will receive a 250cc dose of investigational FMP250 and subjects that were randomized into the investigational group will receive a 250cc dose of placebo FMP250.

Once the FMP250 has been thawed, it is stable for administration for up to 4 additional hours at room temperature or 8 hours refrigerated.

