12.4.3 Analysis of Exploratory Endpoints

1. Alterations in microbial profiles as defined by sequence of genetic material from fecal material
 - a. Sample collection
 1. Up to 60cc of the recipient stool will be collected at the time of procedure.
 2. Up to 60cc of recipient stool will be collected at 4 and 8 weeks of follow up (as per protocol).
 3. Samples will be aliquoted and stored at -80C for batched analysis.
 - b. Sequencing
 1. Fecal DNA extraction
 1. Fecal DNA will be extracted via phenol chloroform, a commercially available resin binding column.
 2. DNA will be stored at -80C until sequencing.
 3. 16S rRNA amplicon libraries will be prepared for analysis by Illumina MiSeq or HiSeq or Roche 454 high throughput sequencing.

4. Genomic DNA libraries will be prepared using Illumina library preparation for sequencing on Illumina MiSeq or HiSeq.
5. Metabolomic analysis by mass spectrometry
6. Microbial strains will be isolated for genomic and functional analysis in vitro and in mouse models

2. Alterations in immune cell function from mucosal biopsies as defined by RNA sequencing and flow cytometry
 - a. Sample collection: 4 biopsies will be collected into sterile saline for cellular analysis
 - b. Biopsy will be removed of IEL fraction with dithiothreitol (DTT) followed by EDTA. Remaining tissue will be digested with collagenase and DNase and purified over a discontinuous percoll gradient to obtain lamina propria mononuclear cells.
 - a. Stimulated and unstimulated will be analyzed by flow cytometry, transcriptional regulation, and cytokine production (including ELISA, cytometric bead array, or Luminex).
 - c. Biopsy will be transferred to DNA extraction buffer and mechanically homogenized. Total DNA will be extracted by phenol chloroform as above. 16S library preparation and sequencing will be performed to determine mucosal associated bacteria

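### Baseline research stool can differ between arms through sampling alone, because its collection window depends on psyllium assignment and the sections on its timing conflict

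*Combined protocol and SAP*

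**What the plan says.** All references are to the combined protocol and SAP.

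- **Section 6.1.1**, on research stool and blood: "This can be collected anytime during the screening period or on the day of the screening colonoscopy", in either case ahead of the FMT. The exception follows at once: "if the subject is randomized to receive psyllium fiber, then this should be collected before day -3 when they begin the fiber supplementation".
- **Sections 6.1.1 and 6.1.2** place randomization at the screening visit, so assignment is known before the sample need be taken.
- **Section 7.8.1**: "Prior to colonoscopy subjects will be asked to undergo bowel prep and to fast the night before the procedure".
- **Section 6.1.2.1** (day 0) has stool and blood taken then if screening did not yield them. It makes no exception for psyllium subjects.
- **Section 12.4.3**: "Up to 60cc of the recipient stool will be collected at the time of procedure". The protocol summary and section 1.2.3 likewise put the pre-FMT stool at day 0 for everyone. Table 1 shows one band running from screening to day 0 for all subjects.
- **Section 9.2.1.1** uses the pre-FMT stool twice. It enters paired Wilcoxon tests of Bray-Curtis similarity between donor, pre-FMT and post-FMT samples. It also determines which strains are dropped, as already common to donor and recipient, before engraftment is counted.

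I found no provision to record preparation status at sampling, and no analysis that takes account of it.

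**The concern.** Under section 6.1.1 the randomized assignment itself decides who may be sampled on day 0. Randomization cannot balance a difference that assignment creates. Section 3.1 gives psyllium to all of Group 2 and none of Group 1, so any imbalance lies along the FMT+psyllium v FMT-alone contrast.

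That contrast carries the mechanistic question. Sections 2.4 and 3.1 make the effect of fiber on engraftment part of the study goal and hypothesis, although the microbiome endpoints are classed as exploratory. If the two arms' baselines come from differently prepared bowels, a difference in pre-to-post change, or in the number of strains counted as engrafted, could reflect sampling and not psyllium. Once the samples are collected, comparability cannot be restored.

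**Working it through.** The plan gives no figure on this point to reproduce, so the main check sets the sections side by side.

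**Step 1. Status of the baseline stool under each rule**

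| Rule | No-psyllium subjects | Psyllium subjects |
|---|---|---|
| 6.1.1 | Screening (before preparation) or day 0 (after preparation) | Before day -3: before fiber and preparation |
| 6.1.2.1 | Day 0 if not yet collected | Same; day 0 would follow fiber and preparation |
| Summary, 1.2.3, 12.4.3 | Day 0 or at the procedure | Same; after about three days of fiber |

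The first rule can make arms differ by preparation. The third equalizes preparation but samples psyllium subjects on fiber, which the exception in 6.1.1 is there to prevent. None of them gives every arm a baseline free of both.

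**Step 2. Count exposed, if 6.1.1 is followed.** Arm sizes are 45 each (protocol summary). Post-preparation baselines: 0 of 45 in FMT+psyllium, and anywhere from 0 to 45 of 45 in FMT alone. In Group 3, half receive psyllium, so 45/2 gives about 22 or 23 subjects on each side. Those subjects receive no donor material before week 8, so only their general pre-to-post change is exposed up to then, not donor engraftment.

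**Step 3. Which analyses use the baseline stool.** The pre-FMT similarity comparisons, the shared-strain removal and any model built on them do. Donor v post-FMT similarity does not. The Mayo score does not.

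**Step 4. Direction.** Suppose preparation lowers the number of detectable recipient strains (an assumption). Fewer strains would then be recognized as shared with the donor and removed in FMT-alone subjects, and apparent engraftment there would be inflated. The opposite assumption reverses the sign. The documents support neither.

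**Step 5. Illustration of size.** Two quantities are assumed because the documents give neither: *q*, the share of FMT-alone subjects sampled on day 0, and *d*, the shift that preparation causes in a baseline measure, in SD units. With 45 v 45 and a two-sided 0.05 test:

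- expected arm difference = q × d
- SE = √[1/45 + (1 + q(1 − q)d²)/45]
- chance of a spurious baseline difference = Φ(qd/SE − 1.96) + Φ(−qd/SE − 1.96)

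Example, q = 0.5 and d = 0.5: the difference is 0.25 SD; SE = √(2.0625/45) = 0.214; 0.25/0.214 = 1.17; the chance is 0.215.

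| q | d = 0.25 | d = 0.5 | d = 0.8 |
|---|---|---|---|
| 0 | 0.050 | 0.050 | 0.050 |
| 0.25 | 0.060 | 0.090 | 0.151 |
| 0.5 | 0.091 | 0.215 | 0.447 |
| 0.75 | 0.144 | 0.420 | 0.789 |
| 1 | 0.220 | 0.660 | 0.967 |

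This describes a between-arm test at baseline, not the paired Wilcoxon tests that section 9.2.1.1 plans. It shows how the problem scales with *q* and *d*; it is not an estimate. One common pre-preparation window sets q = 0 and returns the rate to 0.05.

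**The case against.** A reader might infer that the baselines will differ, that every engraftment result is biased, or that the trial's main result is at risk. The documents do not support any of these.

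- Day-0 collection is permitted, not required. The range of 0 to 45 includes no difference at all.
- It is not established that all 45 FMT+psyllium baselines will precede preparation. Section 6.1.1 says only that they should, and section 6.1.2.1 lets any unsampled subject be sampled on day 0.
- Nothing in the documents says that preparation changes the sequencing measures, or in which direction.
- Donor v post-FMT similarity needs no baseline stool.
- Week-8 Mayo response and its power are untouched.

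There is also a partial safeguard. Mucosal biopsies are taken at the day-0 colonoscopy in every arm, and section 12.4.3 plans 16S sequencing of mucosa-associated bacteria. That baseline has the same preparation status throughout, although psyllium subjects will have had about three days of fiber. A lighter remedy, recording preparation status and running a sensitivity analysis, is also available.

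These limits stand, and they confine the point to possible bias in exploratory stool analyses. They do not remove an assignment-dependent sampling rule or the conflict between sections. The lighter remedy alone would reveal an imbalance without preventing it; if most FMT-alone baselines were post-preparation, excluding them would leave little to compare.

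**Conclusion.** The point holds in a limited form. Following section 6.1.1 can produce baseline stool that differs between FMT+psyllium and FMT alone because of sampling alone: up to 45 of 45 post-preparation samples in one arm against none in the other. Following the summary and sections 1.2.3 and 12.4.3 instead would put psyllium subjects' baseline after fiber has started. The sections must be reconciled whichever rule was intended.

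Actual bias rests on two assumptions that the documents do not settle: that some no-psyllium subjects are sampled on day 0, and that preparation alters the stool measures. Its size and sign are unknown. The exposed results are the exploratory pre-to-post comparisons and the shared-strain removal. The change is worth making because engraftment is part of the stated hypothesis and the remedy is cheap.

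**What to change.** 1. Require baseline research stool from every subject, whatever the arm, in one window before psyllium starts and before bowel preparation. Screening extends to day -3, the day psyllium begins, so provide for subjects screened that day: collection before the first psyllium dose, or at the equivalent time in no-psyllium subjects.
2. Delete the day-0 stool option in sections 6.1.1 and 6.1.2.1, and align the protocol summary, section 1.2.3, section 12.4.3 and Table 1.
3. Record the collection date and preparation status of each baseline stool.
4. Add a sensitivity analysis that excludes any baseline stool taken after preparation or after psyllium began.
5. For blood, only reconcile the timing across the sections. No case is made that preparation affects the blood measures.

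**Cost.** Mostly wording, since psyllium subjects are already asked to meet the earlier window. No-psyllium subjects lose the day-0 convenience. Some may need a home or mailed collection, for which section 6.1.4 already describes a procedure under its COVID-19 modifications. The baseline stool may be up to 28 days old at FMT.

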6.1.2 Treatment Phase

Eligible subjects will be randomly assigned to one of the three (Placebo or Investigational FMP250 +/- Psyllium) treatment groups. A series of randomized blocks of fixed size will be generated with a 1:1:1 allocation ratio. This will provide assurance that after a given block has completed subject enrollment, there will be the same number of subjects assigned to each of the three study arms.

Treatment assignment will be done during the screening visit because participants randomized to receive fiber supplementation must be provided two psyllium bottles to begin consumption 3 days prior the colonoscopy.

6.1.2.1 Screening Colonoscopy (Baseline, Week 0 Day 0)

- Urine pregnancy test as standard of care
- Standard of Care Colonoscopy for diagnostic purposes
 1. Mucosal biopsies taken for diagnostic and research purposes
- FMT delivery by colonoscopy for research purposes

1. If active disease, study physician will blindly administer placebo or investigational FMP250
- Stool and blood samples taken for research purposes, if not previously collected during screening period (days -28 to -3).

6.1.2.2 Clinic Visit 3 (Week 8 ± 5 day(s))

- Medical history (AE evaluation)
- Medication history
- Physical exam
- Urine pregnancy test for research purposes
- Flexible Sigmoidoscopy for diagnostic purposes
 1. Mucosal biopsies taken for research purposes
 2. Subjects in placebo group blindly receive investigational FMP250 .
 3. Subjects in investigational groups blindly receive placebo FMP250
- Stool and blood samples taken for research purposes
- Standard of Care Testing
 1. Fecal Calprotectin
 2. Serological CBC, ESR, CRP, and CMP

6.1.3 Follow-up Phase

6.1.3.1 Phone Consults (+/- 2 days)

- Day 1
- Week 2
- Week 6
- Week 10
- Every subsequent 6 months for the next year

6.1.3.2 Clinic Visits

- **Visit 2 (Week 4 ± 3 day(s))**
 - Medical history (AE evaluation)
 - Medication history
 - Physical exam
 - Stool and blood samples taken for research purposes
- **Visit 4 (Week 12 ± 5 day(s))**
 - Medical history (AE evaluation)
 - Medication history
 - Physical exam
 - Stool and blood samples taken for research purposes

6.1.4 COVID-19 Study Modifications

If necessary, video visits will be recorded in the deviation log and will be submitted to the IRB at the continuing review. Additionally, sample collection for research purposes may also be obtained by having essential research personnel mail the subject a 'Fedex clinical pak' prepackaged for exempt human specimen and provided with mailing instructions via phone. All shipping associated costs will be paid for by the research study's account and a Fedex pick up from the subject's home will be arranged to support "social distancing" practices. As per Fedex recommendations, the subject will leave the package on their door step to minimize interaction with essential Fedex personnel.

7. Study Intervention

7.1 Study Intervention/Device Description

7.1.1 Investigational and Placebo FMP250

The proposed intervention will deliver 250 milliliters of FMP250 by colonoscopy to the investigational FMP250 treatment groups at day 0. The placebo treatment group will instead receive the placebo FMP250 by colonoscopy at day 0 and then the investigational FMP250 by flexible sigmoidoscopy at week 8.

Investigational FMP250 is biologically active human fecal material that is pre-screened, tested, quarantined, stored, packaged, and labeled by OpenBiome. Placebo FMP250 is a control unit made of glycerol, saline, and food dye that is stored, packaged, and labeled identically to the investigational FMP250, to ensure blinding during delivery. Weill Cornell Medicine has contracted OpenBiome to supply 135 investigational FMP250 and 135 Placebo FMP250 directly to the [name] laboratory at Weill Cornell Medicine over the course of the study.

7.1.2 Psyllium Husk Powder

All subjects assigned to the fiber treatment arms will be required to take 1 teaspoon (approximately 5 grams) of psyllium husk powder twice a day (morning and night) for 8 weeks, beginning 3 days prior to Week 0 screening colonoscopy. To simplify, enrolled participants will consume approximately 10g of psyllium per day for 59 days.

The FDA characterizes psyllium seed husk as the dried form of a psyllium seed coat³³.

7.2 Availability

FMP250 is an investigational drug that will be purchased by WCM investigators from OpenBiome.

Psyllium Husk Powder, Organic is an FDA approved prebiotic fiber product that will be commercially sourced from NOW® Foods by WCM investigators for the purpose of our study. Any of the following information provided about their prebiotic product is accessible on their website: <https://www.nowfoods.com/supplements/psyllium-husk-powder-organic>.

7.3 Acquisition and Accountability

Psyllium Ordering and Shipping – Investigator-appointed Weill Cornell research staff will order *Psyllium Husk Powder, Organic* 12 oz. bottles, Item# 5966, UPC# 733739059666. This unit size

contains sufficient psyllium for the four-week psyllium regimen, therefore each subject will receive two bottles for the required 8 week supplementation. Details regarding the ordering and shipping process will depend on the company selected to commercially supply this product. Bulk shipments will be ordered preceding subject enrollment into the study. The quantity of units will be determined by the availability of the commercial provider.

Psyllium Inventory Records – The research coordinator for this study will maintain a careful record of the inventory. This included product arrival dates, expiration dates, lot numbers, and each unit's subject assignment on a *Psyllium Tracking Log*. This form is required by the FDA, must be kept in a safe place and filled out for all units in the possession of the investigator and/or appointed staff. An example of this form is shown below:

PSYLLIUM HUSK POWDER (FIBER SUPPLEMENT) LOG				
IRB Protocol #: 19-04020045	Investigator Name: [name]			
IND #: 19087				
Date	Subject ID #	Lot #	Expiration Date	Study Coordinator Initials

FMP250 Ordering and Shipping – Investigator-appointed Weill Cornell research staff will order units of Investigational or Placebo FMT material by either (1) submitting orders via an OpenBiome specialized online order [form](#), or (2) placing shipment orders directly via phone calls or emails with the OpenBiome Clinical Research Associate assigned to the trial.

OpenBiome Clinical Research Associates:

[name]
P. [contact] ext. 794
[E. [contact]](mailto:[contact])

[name]
[E. [contact]](mailto:[contact])

The initial shipment will need approximately 4-6 weeks to fill due to the internal review process of the study protocol, IRB approval, IND approval, and fully-executed contract conducted at OpenBiome. Upon approval, all subsequent shipments of the study agent will be expected to arrive 5-7 days after the original order is placed.

FMP250 Inventory Records – Investigator-appointed Weill Cornell research staff will maintain a careful record of the inventory and disposition of all agents received from OpenBiome with the *Material Tracking Log*, an example is pictured below, provided with each shipment by OpenBiome. This form should be kept in a safe space and must be filled out for all units. Once completed, it must be returned to OpenBiome prior to ordering the next shipment.

A	B	C	D	E	F	G	H	I
Item	Unit ID	Expiration Date	Ship Date	Date Received	Frozen on Receipt	Unit Status	Administering Physician	Follow-Up Form Given to Physician
FMP250	0001-0001-01	2/16/15	8/16/14		 Yes  No	 Used  Destroyed		 Yes  No

7.4 Formulation, Appearance, Packaging, and Labeling

7.4.1 Investigational FMP250 Formulation and Appearance

Investigational FMP250 is 25 grams of pre-screened and tested human donor stool diluted and homogenized in 12.5% glycerol and normal saline buffer. The solution is then filtered to 330 microns and aliquoted directly into sterile 250mL high-density polyethylene bottles.

Potential OpenBiome donors are extensively screened for eligibility prior to stool collection by completing an informed consent, a Donor Health Questionnaire (DHQ), an in-person interview, and a clinical examination by one of their healthcare professionals. During this eligibility screening, OpenBiome evaluates the potential donor's infectious risk factors, potential microbiome-mediated conditions, general health status, in addition to their breastfeeding status and risk for pregnancy. If patients have completed and satisfied the requirements, OpenBiome then requires serological, stool, and nasal swab testing to be conducted.

There is an extensive standard operating procedure, which can be found in the OpenBiome IB, that is followed to ensure production and process controls. Therefore, once these have been fulfilled, the filtered stool is aliquoted, labelled, and frozen at -20 and then to -80 degrees Celsius. Donor stool is collected at the beginning of a 60-day window and is not shipped for clinical use until the donor undergoes the screening process again. This secondary screening process requires the donor to be cleared by two clinicians, and their stool to be evaluated by a quality assurance officer at the end of the collection window. Donors satisfying all secondary screening criteria will be cleared for stool shipment.

7.4.2 Placebo FMP250 Formulation and Appearance

Placebo FMP250 is a placebo control unit made of a sterile-filtered solution with 12.5% glycerol and normal saline buffer in addition to added brown food dye. Once the placebo ingredients are homogenized, the solution is sterile filtered through a .02um inline filter and aliquoted directly into sterile 250mL high-density polyethylene bottles. Bottles are labelled with a unique identifier and stored at -80°C storage until the placebo lot has passed bioburden testing at which point material is released for use in clinical research trials. Considering the placebo product is masked by food coloring, it should be indistinguishable from the investigational FMP250 by appearance.

7.4.3 *Psyllium Husk Powder, Organic Formulation and Appearance*

This product is comprised of organic soluble fiber from powdered psyllium seed husks. This commercially available fiber supplement is also corn-free, dairy-free, egg-free, gluten-free, sugar-free, soy-free, nut-free, non-GMO, kosher, low sodium, organic and vegan/vegetarian. Natural color variation (beige to light brown) may be different between different units.

7.4.4 Product Labeling and Documentation

OpenBiome's IB indicates that each sample bottle is labeled with (1) the handling and storage warnings, (2) a lot number and (3) the expiration date based on the storage temperature (pictured below from left to right). The lot number is formatted as XXXX-YYYY-ZZ, where XXXX is the donor number, YYYY is the donation number, and ZZ marks the bottle number. Additionally all donor screening results will be provided in the stool shipment. Released placebo units are affixed with the same label as active FMP250 units, though the specialized lot numbers will allow for differentiation.

[figure not shown]

NOW® Foods brands each Psyllium Husk Powder, Organic plastic bottle with the following label. The label provides nutritional facts, suggested usage, ingredients, and a bar code for commercial use in addition to other details. The lot number and the expiration date are printed at the bottom of each individual unit (not pictured below).

